12.3.2. Statistical Analysis

POM plasma concentrations will be listed and summarized by cycle using descriptive statistics (N, mean, SD, coefficient of variation [CV%], geometric mean, geometric CV%, median, Min, and Max). Box-Whisker plot of POM plasma concentrations will be generated.

[REDACTED]

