12.2. Analysis population

As a data cut-off date of May 4th 2015, all subjects who receive POM and have PK data will be included. If any subjects are found to be noncompliant with respect to dosing, or encounter other circumstances that could affect the evaluation of PK, a decision will be made on a case-by-case basis as to their inclusion in the PK analysis. Data excluded from PK analysis and/or statistical analysis will be included in the data listings, but not in the summaries.

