12.3. Pharmacokinetic Analysis

12.3.1. Data handling

Pre-dose concentrations that are below the limit of quantification (BLQ) or missing will be assigned a number value of zero.

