Appendix B: Tables Graphs and Listings

Tables Section 14.

Table Number	Table Title
14.1.1	Analysis Populations
14.1.2.1	Subject Disposition – Treatment Phase: All Populations
14.1.2.2	Subject Disposition – Long-term Follow-up Phase: All Populations
14.1.3	Summary of Reasons for Screen Failure: Screen Failure Subjects
14.1.4	Subjects Enrolled by Study Site: Intention to Treat Population
14.1.5	Summary of Protocol Violations: Intention to Treat Population
14.1.6	Summary Demographic and Baseline Characteristics: All Populations
14.1.7	Baseline Disease Characteristics: All Populations
14.1.8	Medical History: All Populations
14.1.9	Prior Cancer History: All Populations
14.1.10	Prior Medications: All Populations
14.1.11	Prior Therapies: All Populations
14.1.12	Summary of Prior Anti-myeloma Therapies by Drug Class: All Populations
14.1.13	Summary of Last Prior Anti-myeloma Therapies by Drug Class: All Populations
14.1.14	Refractory Status to Selected Prior Anti-myeloma Therapies: All Populations
14.1.15	Summary of Prior Anti-myeloma Treatment Lines and Regimens: All Populations
14.1.16	Evidence of Progression Status to Last Anti-myeloma Therapies: All Populations
14.1.17	Prior Cancer Surgeries for this Disease: All Populations
[REDACTED]	[REDACTED]
14.1.19	Prophylactic Medications During the Treatment Period: Safety Population
[REDACTED]	[REDACTED]

14.1.21	Summary of Prior Venous Thromboembolic Events: All Populations
14.1.22	Summary of Cytogenetic Data: All Populations
14.2.1.1	Summary of Overall Response and Response Rates: All Populations
14.2.1.2	Overall Survival Follow-up: All Populations
14.2.2	Summary of Time to Response (TTR): All Populations
14.2.3	Summary of Duration of Response (DoR): All Populations
14.2.4	Summary of Time to Progression (TTP): All Population
14.2.5.1	Summary of Progression Free-Survival (PFS): According to EMA Guidelines: All Populations
14.2.5.2	Summary of Progression Free-Survival (PFS): According to FDA Guidelines: All Populations
14.2.6	Summary of Overall Survival (OS): All Populations
14.2.7	Summary of Subsequent Anti-myeloma Therapy: Intention to Treat Population
14.2.8	Summary of CC-4047 Plasma Concentrations (ng/mL) by Cycle: Pharmacokinetic Population
14.3.1.1	Summary of Treatment Duration: Safety Population
14.3.1.2.1	Summary of Dose Information: Safety Population
14.3.1.2.2	Summary of Dose Information by Cycle: Safety Population
14.3.1.3.1	Summary of Dose Reductions: Safety Population

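### Pre-dose pomalidomide concentrations set to zero cannot enter the geometric mean and geometric CV% that the SAP plans for the same data

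*SAP*

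**What the plan says.** SAP section 12.3.1 (Data handling) gives one rule: "Pre-dose concentrations that are below the limit of quantification (BLQ) or missing will be assigned a number value of zero".

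SAP section 12.3.2 (Statistical Analysis) follows directly: "POM plasma concentrations will be listed and summarized by cycle using descriptive statistics". The statistics listed are "N, mean, SD, coefficient of variation [CV%], geometric mean, geometric CV%, median, Min, and Max". No time points are named, and no sentence separates pre-dose samples from others.

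The output is Table 14.2.8 in Appendix B, "Summary of CC-4047 Plasma Concentrations (ng/mL) by Cycle: Pharmacokinetic Population".

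The only readable route out of the PK summaries is in section 12.2. It covers dosing non-compliance and other circumstances that could affect the PK evaluation, decided case by case, and ends: "Data excluded from PK analysis and/or statistical analysis will be included in the data listings, but not in the summaries". It does not deal with BLQ values or zeros.

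**The concern.** Sections 12.3.1 and 12.3.2 are adjacent and apply to the same concentrations, but they do not work together. A geometric mean is the exponential of the average logarithm, and the geometric CV% comes from the variance of the logarithms. The logarithm of zero does not exist, so the data rule produces values that two of the listed statistics cannot use.

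The programmer must then choose without guidance. If the zero is kept, the table shows a geometric mean of 0 and no geometric CV%. If it is dropped, the geometric columns describe only quantifiable samples, while N, mean, SD and median still include the zeros. A reader of Table 14.2.8 could not tell which was done.

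The rule also turns missing pre-dose values into zeros. A sample that was never measured would then cause the same failure, and would lower the arithmetic mean as well.

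**Working it through.** **Inputs from the SAP.** The zero rule (12.3.1), the list of statistics (12.3.2), and the absence in the readable text of any rule that keeps zeros out of them. The SAP gives no lower limit of quantification (LLOQ), BLQ share, concentration level or CV, so there is no stated figure to reproduce.

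**Formulas.** Geometric mean = exp(mean of ln x). Geometric CV% = 100 × √(exp(variance of ln x) − 1).

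**1. One zero in five values (invented data: 0, 4, 8, 10, 16).**
- Zero kept: the geometric mean is (0 × 4 × 8 × 10 × 16)^(1/5) = 0. The variance of the logs does not exist, so the geometric CV% is undefined.
- Zero dropped: the geometric mean is (4 × 8 × 10 × 16)^(1/4) = 5120^(1/4) = 8.46. The log-variance is 0.333, so the geometric CV is √(exp(0.333) − 1) = 62.8%, on n = 4.
- The arithmetic mean beside it is 38/5 = 7.6, on n = 5.

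This part needs no assumption beyond a single zero in a cycle.

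**2. Bias if true on-treatment values are BLQ and dropped (illustration).** Assume log-normal concentrations whose lowest fraction f is BLQ. Let s = √(ln(1 + CV²)), z = Φ⁻¹(f) and m = φ(z)/(1 − f). The geometric mean is inflated by exp(s·m). The log-variance becomes s²(1 + z·m − m²).

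- f = 10%: z = −1.282, m = 0.195, variance factor 0.712.
- f = 20%: z = −0.842, m = 0.350, variance factor 0.583.
- CV 60%: s = 0.555. CV 100%: s = 0.833.

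| True CV | f | Geometric mean ratio | Geometric CV after dropping |
|---|---|---|---|
| 60% | 10% | exp(0.555 × 0.195) = 1.11 | 49% |
| 60% | 20% | exp(0.555 × 0.350) = 1.21 | 44% |
| 100% | 10% | exp(0.833 × 0.195) = 1.18 | 80% |
| 100% | 20% | exp(0.833 × 0.350) = 1.34 | 71% |

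**3. The handling rule matters in both directions.** In a simulation of 200,000 log-normal values (median 10, log-SD 0.6; geometric mean 9.99, geometric CV 65.7%):

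| BLQ share | Zeros kept | BLQ dropped | BLQ set to LLOQ/2 |
|---|---|---|---|
| 10% | 0 / undefined | 11.2 / 53.9% | 9.6 / 75.7% |
| 20% | 0 / undefined | 12.3 / 48.2% | 9.3 / 78.9% |

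In this example, substitution pulls the geometric mean slightly down and the CV up, so it is not neutral either.

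**4. Missing values set to zero.** If a share q of values is missing at random, the expected arithmetic mean is multiplied by 1 − q, for example 0.90 at 10%.

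**The case against.** The strongest answer is that the rule may exist out of sight. A redacted block follows the sentence in section 12.3.2, and section 12 sends all PK tables, figures and listings to a separate delivery document. This stands as a limit. The conflict is in the readable text, and one cross-reference would settle it if a rule exists.

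A second answer is that programmers routinely drop zeros. But that is an unstated choice, and it leaves one N printed beside statistics from two sample sets.

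Three stronger readings are tempting, and the SAP does not support them:

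- *BLQ values are expected by design.* Section 8.6 implies 21 dosing days in a 28-day cycle, so a reader might infer that Day 1 pre-dose samples follow a week without drug. The SAP gives no PK sampling times; pre-dose samples on later dosing days would fit section 12.3.1 equally well.
- *The 11–34% is the bias in this trial.* It applies only where a minority of true on-treatment values is censored. Before the first dose the true value is zero, and leaving such a sample out of a geometric mean is not a bias. After a long drug-free gap most samples might be BLQ, and the illustration would not apply.
- *Trough exposure, or the exposure–response analysis, would be wrong.* Section 12.3.2 does not mention troughs, and section 13 takes Cmin and the other exposure metrics from the population PK analysis. Mean, SD, median, minimum, maximum and the box plot remain computable, although missing values set to zero would still distort them.

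**Conclusion.** The point holds as an inconsistency between two adjacent rules. In the readable text, one pre-dose zero in a cycle makes the geometric mean 0 and leaves the geometric CV% undefined (undefined, not zero). If the zero is dropped without saying so, the two geometric statistics use fewer samples than the N, mean and median beside them.

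Where a minority of true on-treatment values is BLQ and dropped, the geometric mean is too high and the geometric CV too low. The 11–34% range for the geometric mean rests on an assumed log-normal shape, 10–20% BLQ and a CV of 60–100%. The actual size cannot be computed from the SAP.

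The consequence is limited to the descriptive Table 14.2.8. Neither the primary safety endpoint nor any efficacy endpoint depends on it. It is a minor point, worth correcting because the correction is cheap.

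**What to change.** In section 12.3.1, treat missing pre-dose concentrations as missing, not zero. A sample before the first dose may stay zero.

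In section 12.3.2:
- Leave samples taken before the first dose out of the geometric mean and geometric CV%.
- For later BLQ samples, do not enter zero into these two statistics. Name one prespecified method, for example a left-censored log-normal estimate or LLOQ/2. Which one is a matter of choice; fixing it in advance is what matters.
- Print in Table 14.2.8 the number and percentage BLQ, and the n used for the geometric statistics.

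If the redacted text or the PK delivery document already holds such a rule, a cross-reference is enough for the geometric statistics. The treatment of missing values in section 12.3.1 should still be checked against it.

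The cost is a few sentences of SAP text and slightly more programming. Geometric statistics may not be shown for cells that are mostly BLQ.

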13. EXPOSURE-RESPONSE ANALYSIS

All analyses related to PK/PD data will be reported separately from the clinical study report.

[REDACTED]

The key exposure data are serum drug concentration, C_{max}, C_{min} and AUC derived from the population PK analysis. The key efficacy and safety endpoints include AEs, ORR, time to response, DoR, PFS, TTP, and OS. Other efficacy and safety endpoints may also be explored, as appropriate.

[REDACTED]

APPENDICES

Appendix A: Date Imputation Guideline

Impute Missing AE / Prior or Concomitant Medications Start Dates:

If the stop date is non-missing and the imputed start date is after the stop date, the stop date will be imputed by the stop date.

Missing day and month with non-missing year

- If the year is the **same** as the year of first day on the IP, then the day and month of the start date of the IP will be assigned to the missing fields
- If the year is **prior to** the year of first day on the IP, then December 31 will be assigned to the missing fields.
- If the year is **after** the year of first day on the IP, then January 1 will be assigned to the missing fields.

Missing day only

- If the month and year are the **same** as the year and month of first day on the IP, then the start date of the IP will be assigned to the missing day.
- If the month and year are **before** the year and month of first day on the IP, then the last day of the month will be assigned to the missing day.
- If the month and year are **after** the year and month of first day on the IP, then the first day of the month will be assigned to the missing day.
- If the stop date is non-missing and the imputed start date is after the stop date, the start date will be imputed by the stop date.

Missing year

- Not imputed. Included as TEAE.

Impute Missing AE / Prior or Concomitant Medications Incomplete Stop Date:

If the imputed stop date is before the start date then the imputed stop date will be equal to the start date.

Missing day and month with non-missing year

- If the year of the incomplete stop date is the **same** as the year of the last dose date of the IP, then the day and month of the last dose date will be assigned to the missing fields.

- If the year of the incomplete stop date is **prior to** the year of the last dose date of the IP, then December 31 will be assigned to the missing fields.
- If the year of the incomplete stop date is **after** the year of the last dose date of the IP, then January 1 will be assigned to the missing fields.

Missing day only

- If the month and year of the incomplete stop date are the **same** as the month and year of the last dose date of the IP, then the day of the last dose date will be assigned to the missing day.
- If the month and year of the incomplete stop date are **before** the month and year of the last dose date of the IP, then the last day of the month will be assigned to the missing day.
- If the month and year of the incomplete stop date are **after** the month and year of the last dose date of the IP, then the first day of the month will be assigned to the missing day.

Missing year

- Not imputed. Included as TEAE.

Impute Missing Disease Diagnosis Dates:

For partial diagnosis dates, January will be assigned to the missing month; and the first day of the month will be assigned to the missing day.

Impute Incomplete Prior Evidence of Disease Progression Dates:

For partial prior disease progression dates, the first day of the month shall be imputed.

Impute Missing Dates in Prior Anti-myeloma Regimen:

For each prior anti-myeloma regimens, the regimen start/stop date, disease progression date, best response date, and date of first response for RR or better, will be collected. If the day of any date is missing, then the first day of the non-missing month will be assigned to the missing day; if month or year of the missing date is missing, then the date will not be imputed and treated as missing.

Impute Missing Dates in Subsequent Anti-myeloma Therapy:

Subjects will be allowed to take other anti-myeloma therapy after discontinuation from the study. The anti-myeloma therapy start/stop date will be collected. If the day of any date is

missing, then the last day of the non-missing month will be assigned to the missing day; if day and month are both missing, the December 31 of the non-missing year will be assigned to the missing day.

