4.1.1. Dates Handling

Dates will be stored as numeric variables in the SAS analysis files and reported in DDMMMYYYY format (i.e., the [Date9](#). datetime format in SAS). Dates in the clinical database are classified into the categories of procedure dates, log dates, milestone dates, outcome dates, and special dates.

- **Procedure Dates** are the dates on which given protocol-specified procedure are performed. They include the dates of laboratory testing, physical examinations, tumor scans, etc. They should be present whenever data for a protocol-specified procedure is present and should only be missing when a procedure is marked as NOT DONE in the database. Procedure dates will not be imputed.
- **Log Dates** are dates recorded in the case report form (CRF) data logs. Specifically, they are the start and end dates for AEs and concomitant medications/procedures. They should not be missing unless an event or medication is marked as *ongoing* in the database. Otherwise, incomplete log dates will be imputed according to the rules in Appendix A of this SAP: Date Imputation Guideline (e.g., for duration or cycle assignment etc.). However, in listings, log dates will be shown as recorded without imputation.

- **Milestone Dates** are dates of protocol milestones such as enrollment date, study drug start date, study termination, etc. They should not be missing if the milestone occurs for a subject. They will not be imputed.
- **Outcome Dates** are dates corresponding to study endpoints such as survival, disease progression, etc. In most cases they are derived either from a milestone (e.g., the survival date is derived from the death date), or a procedure date (e.g., the progression date is derived from the date of the tumor scan that was used to determine progression). They may be subject to endpoint-specific censoring rules if the outcome event, for instance, did not occur; otherwise they are not subject to imputation.
- **Special Dates** cannot be classified in any of the above categories and they include, for example, the date of birth. They may be subject to variable-specific censoring and imputation rules (see Section 4.1.2. below).

Dates recorded in comment fields will not be imputed or reported in any specific format.

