11.1.1. Adverse Events

Adverse Events will be coded according to the Medical Dictionary for Regulatory Activities (MedDRA) version 15 or higher. The severity of AEs will be graded according to the NCI CTCAE version 4.0. Summaries will be by system organ class and preferred term.

Treatment-emergent AEs (TEAEs) are defined as any AE occurring or worsening on or after the first treatment of the IP and within 28 days after the last dose. If a subject experiences the same preferred term multiple times then the event will be counted only once and by the greatest severity.

All TEAEs, TEAEs leading to IP discontinuation, TEAEs leading to dose reduction/interruption, TEAEs related to the IP, serious TEAEs, serious TEAEs related to study medication, and serious TEAEs leading to study medication discontinuation will be summarized by system organ class and preferred term. Summary of TEAEs with NCI-CTCAE grade 3 or 4 and with NCI-CTCAE grade 5 will also be provided. Summary of TEAEs by dosing cycle will also be provided. Where necessary, adverse events will be categorized by using specified MedDRA hierarchy terms (i.e., SOC, HLGT, HLT, and PT), and/or by Standardized MedDRA Queries (SMQs); the number and percentage of subjects with adverse events alone and/or with concurrent events, medical history, medications, laboratory values, etc., may be tabulated, and where possible, may be organized or displayed by specific parameters (e.g., time to occurrence, other demographics, exposure/duration/cycle, therapy period(s), etc.) . Where necessary, and as the data allow, incidence rates will be calculated, summarized and displayed.

If a subject experiences the same preferred term multiple times then the subject will be counted only once by the greatest severity of that term when presented in tabulations.

An AE listing will be presented separately for individual subjects.

Adverse Events of Special Interest

Analysis of AEs of special interest will be presented with tabulations for: TEAEs of interest, NCI-CTCAE grade 3 or 4 TEAEs of interest, TEAEs of interest related to study medication, serious TEAEs of interest and TEAEs of interest leading to study medication discontinuation. The following AE of interest categories and preferred terms include but are not limited to:

- neutropenia
- febrile neutropenia
- infection
- thrombocytopenia
- hemorrhage and bleeding
- neuropathy
- DVT (deep vein thrombosis)
- PE (pulmonary embolism)

- SPM (second primary malignancies)

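### Two date rules in SAP Appendix A, applied as written, can class adverse events that began (and may have ended) before the first dose as treatment-emergent, contrary to section 11.1.1

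*SAP*

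**What the plan says.** SAP section 11.1.1 defines a treatment-emergent adverse event (TEAE) as "any AE occurring or worsening on or after the first treatment of the IP and within 28 days after the last dose". The date on which an event ended plays no part in the definition.

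SAP section 4.1.1 classes AE and medication start and end dates as log dates and says that "incomplete log dates will be imputed according to the rules in Appendix A of this SAP"; dates of events marked as ongoing are allowed to be missing. Appendix A is therefore the operative rule for partial AE dates.

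Appendix A contains these rules:

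- **Start date, day and month missing, same year as first dose:** "the day and month of the start date of the IP will be assigned to the missing fields".
- **General check at the head of the start-date rules:** if the stop date is known and "the imputed start date is after the stop date, the stop date will be imputed by the stop date".
- **Same check, repeated at the end of the day-only rule:** here it reads "the start date will be imputed by the stop date".
- **Start date, year missing:** "Not imputed. Included as TEAE".
- **Stop date, year missing:** the same words again.

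**The concern.** The primary endpoint in SAP section 3.3 is the incidence of adverse events, and most AE tables in Appendix B count treatment-emergent events. An imputation rule may reasonably be cautious when onset is unknown. It should not override a date that is known and that settles the question under section 11.1.1.

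Two rules do that. The missing-year rule for stop dates assigns TEAE status from a date that section 11.1.1 does not use. The general start-date check was evidently meant to pull an impossible imputed start back to the known stop, but as worded it replaces the stop date by itself. In both cases an event that belongs before treatment can enter the treatment-emergent tables.

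**Working it through.** The SAP gives no figure for this point, so the check sets the rules against the definition and then applies them literally.

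**Missing stop year (assumed dates).** First dose 15 June 2013; AE start 1 June 2013, complete; no worsening; stop date recorded without its year.

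- Section 11.1.1: onset before first dose and no worsening, so not a TEAE.
- Appendix A, stop dates: included as a TEAE.
- Section 4.1.3: cycle 1 begins on the first day of any study drug. The known start falls before it, and there is no previous cycle to which the event could be attributed. The event would be a TEAE with no cycle.

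The stop-date rules also cover prior and concomitant medications, for which TEAE status has no meaning. Together with the identical wording under start dates, this suggests that the line was carried over from there.

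**Year-only start (assumed dates).** First dose 15 June 2013; AE start recorded as 2013 only; stop 5 June 2013, complete.

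1. The recorded year equals the year of first dose, so the imputed start is 15 June 2013.
2. The imputed start is later than the stop (15 − 5 = 10 days), so the general check applies.
3. The check sets the stop to the stop, 5 June. Nothing changes.
4. Result: a start on the first-dose date, hence a TEAE in cycle 1 that ended 10 days before it began.
5. With the day-only wording applied instead, the start becomes 5 June 2013, and the event is not a TEAE.

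**Enumeration.** Take every AE that starts and stops within the 28 days before an assumed first dose on 15 June 2013. A start *a* days before dosing (*a* = 1 to 28) allows *a* possible stop days, giving 1 + 2 + … + 28 = 28 × 29 / 2 = 406 start/stop pairs.

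| Recorded start, stop known and before dosing | Classed as TEAE | Imputed start after stop |
|---|---|---|
| Year only, rule as written | 406 of 406 | 406 of 406 |
| Year only, check corrected to reset the start | 0 of 406 | 0 of 406 |
| Day missing only, rule as written | 0 of 406 | none remain, because the check resets the start |

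These are not frequencies. They show that within the stated condition (onset year equal to the year of first dose, day and month unknown, known stop before dosing) the misclassification is certain, and that the corrected check removes it.

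**Missing start year.** The rule counts the event as a TEAE with no reference to the stop date, so an event with a known stop before first dose is also counted. Correcting the general check does not repair this, because no start date is imputed.

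**Size per event.** If the safety population equals the planned 720, one subject wrongly counted adds 1/720 = 0.14 percentage points to the incidence of a preferred term. This holds only if that subject has no genuine TEAE of the same term, because section 11.1.1 counts a subject once per term.

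**The case against.** The strongest reply is that this is editorial. The general check is an obvious misprint: its condition matches that of the correct sentence further down, it heads the whole start-date block, and no programmer could implement it meaningfully. Section 4.1.1 expects log dates to be complete unless the event is ongoing, so the triggering records should be rare. The error runs towards counting too many TEAEs, which is the cautious direction in a safety study. Much of this stands, and it limits the weight of the point. It does not remove the contradiction with section 11.1.1. The missing-stop-year rule is not a misprint with an obvious correct reading, and caution is no reason to set aside a known onset date.

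Some stronger readings are tempting and are not supported:

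- **That counting a missing start year as a TEAE is wrong in itself.** When nothing else is known, it is a defensible conservative default. The fault is only that a known stop before dosing is ignored.
- **That stop dates after the last dose are imputed wrongly,** because they go to the first day of the month or 1 January while earlier ones go to the last day or 31 December. Both follow one principle, the compatible date nearest to the last dose, and the start-date rules work the same way around the first dose. The result is the shortest compatible length for an event that began after the last dose and has a partial stop date. Choosing the latest date would carry the opposite bias. Nothing in the SAP contradicts the convention.
- **That one false TEAE would confirm an infrequent event under section 3.5.** That statement is sample-size reasoning. Section 4.1.4 plans no formal testing, and no analysis decision turns on a single case.
- **That the primary endpoint is materially biased.** Section 3.3 names adverse events, not only treatment-emergent ones, and Appendix B also plans a table (14.3.2.16.16) and a listing (16.2.7.1.2) of events outside the treatment-emergent window. No count of partial dates is available from which to show an effect.

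**Conclusion.** The point holds as a minor one. The stop-date rule contradicts section 11.1.1 whenever the start date is complete and before first dose and the event did not worsen. The general start-date check does nothing as written, so a year-only onset in the year of first dose is counted as treatment-emergent despite a known stop before dosing.

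The conclusion assumes that the rules are programmed literally. It concerns only incomplete dates of events not marked ongoing. The SAP does not say how many such dates there are, so the total effect on AE incidence cannot be computed; it is probably small. The case for correction is that these are operative rules for the main safety tables and that the correction is nearly free.

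**What to change.** Make three edits to Appendix A:

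1. **Stop dates, missing year.** Leave the date unimputed and delete the TEAE clause. State that TEAE status follows onset or worsening as in section 11.1.1. Keeping the worsening limb matters: a pre-dose event that worsens on treatment must still count.
2. **General start-date check.** Change its last clause to "the start date will be imputed by the stop date" and state that it applies to all partial start dates. The repeat under the day-only rule then becomes redundant.
3. **Start dates, missing year.** Keep the TEAE default, but exempt events whose known stop date is before the first dose.

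The cost is the wording and a small programming update. No new data are needed, and nothing changes in design or conduct. The few events affected would move from the treatment-emergent tables to the pre-treatment listing.
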